9.4 APPROPRIATENESS OF MEASUREMENTS

The primary endpoint of the change in LDL-C from baseline is a valid surrogate measure to determine CV risk, as explained in [Section 4](#).

10 STUDY PROCEDURES

The window period for Week 0 is +3 days. The window period for Weeks 8, 12 and 24 is ± 3 days. The window period for Weeks 4, 20, and 32 is ± 7 days.

For all visits after Day 1/inclusion visit, if one visit date is changed, then the next visit should take place according to the original schedule as outlined in the Study Flow Chart ([Section 1.2](#)).

Blood sampling

All blood sampling, including the blood sampling for determination of lipid parameters (eg, TC, LDL-C, HDL-C, TG, non-HDL-C, Apo A, Apo B, Apo C-III, Lp(a), LDL particle size and number) and also for plasma glucose should be performed in the morning, in fasting condition (ie, overnight, at least 10 to 12 hours fast and refrain from smoking), and before IMP injection for all site visits throughout the study. Alcohol consumption within 48 hours and intense physical exercise within 24 hours preceding the blood sampling are discouraged.

Note: if the patient is not in fasting conditions, the blood sample will not be collected and a new appointment will be given to the patient for the day after (or as close as possible to this date), with instructions to fast (see above conditions).

Laboratory tests

The laboratory data are collected in accordance with the study schedule and the details provided in the Study Flow Chart ([Section 1.2](#)).

- Hematology: all visits except Weeks 4 and 20; may be performed at Week 0 as applicable and based on the clinical discretion of the Investigator
- Chemistry: all visits except Visits 3 and 6; may be performed at Week 0 as applicable and based on the clinical discretion of the Investigator, except for plasma glucose which should be performed at Week 0 for all patients
- HbA1c: screening and Weeks 0, 12, and 24
- Lipid panel: screening and Weeks 0, 8, 12, 20, and 24
- Measured LDL-C via beta quantification: Weeks 0, 12, and 24
- Other lipid assessments (Apo B, Apo A-1, Apo C-III, LDL particle size and number, Lp[a]): Weeks 0, 12, and 24
- Liver panel: all visits except Visits 3 and 6; may be performed at Week 0 as applicable and based on the clinical discretion of the Investigator. In case of total bilirubin values above the normal range, differentiation into conjugated and non-conjugated bilirubin will occur automatically
- Creatine Phosphokinase (CPK): all visits except Visits 3 and 6; may be performed at Week 0 as applicable and based on the clinical discretion of the Investigator.

- Hepatitis B surface antigen: screening only.
- Hepatitis C antibody: at screening and Week 24; in case of ALT increase during the study, hepatitis C antibody should be determined. If Hepatitis C antibody is positive during the study, reflexive testing should be performed.
- Pregnancy testing (in women of child bearing potential only): serum pregnancy test at screening only. Urine pregnancy test at Weeks 0 and 24.
- Thyroid stimulating hormone: screening only for patients who are taking thyroid hormone replacement
- C-peptide: screening only
- PCSK9 levels will be performed only at Week 0.
- Anti-alirocumab antibodies (Week 0, Week 12, and Week 24).

Urine samplings

Urinalysis will be performed at screening and Week 24 visits. Dipstick will be performed and will assess for pH, specific gravity, and for the presence of blood, protein, glucose, ketones, nitrates, leukocyte esterase, uro-bilinogen and bilirubin. If the dipstick is abnormal then standard microscopy will be conducted. Microscopy will evaluate for the presence of red blood cells (RBC), RBC clumps, white blood cells (WBC), WBC clumps, epithelial cells (transitional, renal tubular, and squamous), casts (hyaline, epithelial, WBC, RBC, granular, fatty, cellular, broad, waxy), crystals (triple phosphate, calcium oxalate, calcium phosphate, calcium carbonate, uric acid, amorphous, ammonium biurate, bilirubin, leucine, tyrosine, cystine), bacteria, yeast- budding, yeast-hyphae, trichomonas, oval fat body, fat, mucous, and sperm.

Spot urine testing will be performed for albumin and creatinine to calculate the albumin: creatinine ratio at the screening and Week 24 visits.

Notes: Any clinically relevant abnormal laboratory value should be immediately rechecked for confirmation before making any decision for the concerned patient. It should be documented as an AE/AESI/SAE if one or more criteria in [Section 10.4](#) are met.

Decision trees for the management of certain laboratory abnormalities by Sanofi are provided in [Appendix C](#) and should be followed by Investigators.

Physical examination

A general physical examination should be performed at the time points indicated in the study schedule flowchart ([Section 1.2](#)). If a new clinically significant abnormality or worsening from baseline is detected after inclusion, then an AE should be reported and the patient should be considered for further clinical investigations and/or specialist consultation, as per the Investigator's medical judgment.

Blood pressure/heart rate

Blood pressure (BP) should be measured in sitting position under standardized conditions, approximately at the same time of the day, on the same arm, with the same apparatus (after the patient has rested comfortably in sitting position for at least 5 minutes). Values are to be recorded in the e-CRF; both systolic BP and diastolic BP should be recorded. At the first screening visit, BP should be measured in both arms. The arm with the highest diastolic pressure will be determined at this visit, and BP should be measured on this arm throughout the study. This highest value will be recorded in the e-CRF.

[figure not shown]
Heart rate will be measured at the time of the measurement of BP.

Notes: in case of high BP values, the Investigator is responsible for the optimization of the patient's treatment to achieve BP targets as defined by local guidelines/regional standards of care.

Body weight and height

Body weight should be obtained with the patient wearing undergarments or very light clothing and no shoes, and with an empty bladder. The same scale should be used throughout the study.

Height needs to be measured, as self-reported heights are not acceptable.

Insulin log

Patient should be instructed to complete the insulin log in order to record his/her daily insulin dose (for basal insulin and for prandial insulin, as applicable) for at least 7 days prior to each visit, and to bring this information to the next study visit. The patient may record the daily insulin dose for more than 7 days prior to the study visits, however only the information collected for the last 7 days prior to each visit will be entered into the CRF.

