	
Alirocumab will be administered subcutaneously with a starting dose of 75 mg every 2 weeks (Q2W) for 12 weeks with a blinded uptitration to alirocumab 150 mg Q2W at Week 12 if the LDL-C at the Week 8 visit is ≥ 70 mg/dL (1.81 mmol/L). Patients who have an LDL-C < 70 mg/dL (1.81 mmol/L) at the Week 8 visit will continue with alirocumab 75 mg every two weeks until the end of the double-blind treatment period.
 
The study consists of:
 
• A screening period of up to 3 weeks;• A double-blind treatment period of 24 weeks;• A safety observation period (off-treatment) of 8 weeks after the end of the double-blind treatment period. 
Note, the Investigator will need to document in the case report form (CRF) any adverse events (AEs) that have occurred within 70 days of the last dose of IMP that (s)he is aware of. A phone visit will take place at Week 32 in order to ensure documentation of any AEs occurring during this period.
 
Patients should be on a stable diet for glucose and lipid management throughout the entire study duration from screening to the Week 24 visit. There shall be no significant changes in nutritional composition of the diet or in the quantity/pattern of food consumed. Patients must be receiving treatment for diabetes in accordance with local/regional standards of care.
 
Statin dose and dose regimen as well as dose and dose regimen of other lipid modifying treatment(s) (if applicable) should be stable for 4 weeks prior to the screening period and throughout the entire study duration, including from the screening visit to randomization.
 
The data on lipid parameters from blood samples will be masked after randomization. No attempts should be made by the Investigator or patient to have the patient's lipid values independently evaluated after randomization until after the Week 24 visit, except for the safety of the patient as per the Investigator's judgment. At the end of the double-blind treatment period (Week 24 visit), the Investigator will continue to manage the patient's lipids in accordance with standard practice. Any lipid values after randomization (eg, if done for patient safety) should be redacted in the source documents and not shared with the Sponsor.
 
Duration of study treatment will be 24 weeks with the last injection administered at Week 22.
 
Patients will visit the study site at Weeks -3, 0, 8, 12, 20, and 24 with lab work at each visit; in addition phone visits are scheduled at Weeks 4 and 32. Week 8 is a critical visit because it will be the only scheduled visit where an LDL-C value for uptitration will be available.

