ASSESSMENT SCHEDULE	
V1: (Week -3 [Day -21 to -8]): screening, investigational medicinal product (IMP) training, and safety.
 
V2: (Week 0 [Day 1 ±3 days]): baseline, randomization, first administration with double-blind IMP, and safety.
 
V3: (Week 4 [Day 29 ±7 days]): telephone contact
 
V4: (Week 8 [Day 57 ±3 days]); V5: (Week 12, [Day 85 ±3 days]); V6: (Week 20 [Day 141 ±7 days]) (efficacy and safety assessments)
 
V5: (Week 12) Second allocation of double-blind IMP
 
V7: (Week 24 [Day 169 ±3 days]): End of treatment (EOT) visit (efficacy and safety assessments)
 
V8: (Week 32 [Day 225 ±7 days]): telephone contact (safety assessment)
 
If one visit is changed, the next visit should take place according to the original schedule. Note: Patients who prematurely discontinue treatment should be followed as scheduled.

STATISTICAL CONSIDERATIONS	
Sample size determination:
  
Analysis Population:
 
Randomized population includes any patients who have been allocated to a randomized treatment regardless of whether the treatment kit was used or not.
 
The primary efficacy analysis population will be the ITT population, defined as all randomized patients who had an evaluable primary efficacy endpoint.
 
The primary efficacy endpoint will be considered evaluable when both of the following conditions are met:
 
• The baseline calculated LDL-C value is available• At least one calculated LDL-C value is available within one of the analysis windows up to Week 24. 
The mITT population (otherwise referred to as the on-treatment population) is defined as all randomized patients who took at least one dose or part of dose of the double-blind IMP injection and had an evaluable primary efficacy endpoint during the efficacy treatment period.
 
The primary efficacy endpoint will be considered evaluable during the efficacy treatment period when both of the following conditions are met:
 
• The baseline calculated LDL-C value is available

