8.1.2 Timing of administration

During the screening period, patients or the designated person will have to perform a placebo self-injection training using a prefilled pen, before the first IMP injection.

At the randomization visit, the first IMP injection will be done at the site by the patient or another designated person (such as spouse, relative, etc) under direct site staff supervision. Patients will be monitored at the investigational site for at least 30 minutes after this first injection in this study. If the designated person changes during the course of the study, the new designated person will need to be trained with placebo.

IMP subcutaneous injections will then be performed outside of the clinic, Q2W up to the last injection. If the injection is scheduled to take place on the same date as the site visit, then the IMP should be administered after the blood sampling has been completed. In exceptional cases, if a patient prefers to have the injection performed at the study site and provisions are able to be made to accommodate the administration of injections at the site, it may also be allowed.

IMP should be administered subcutaneously Q2W, ideally at approximately the same time of the day; however, it is acceptable to have a window period of ± 3 days. The time of the day is based upon the patient's preference.

If by mistake or due to other circumstances an injection is delayed by:

- more than 7 days from the missed date or completely missed, then the patient should return to the original schedule of IMP administration without administering delayed injections.
- less than or equal to 7 days from the missed date, then the patient should administer the delayed injection and then resume the original schedule of IMP administration.

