9.1.2 Primary safety endpoints

Safety parameters (AEs, laboratory parameters, vital signs) will be assessed throughout the study.

The observation of safety data will be as follows:

- Pre-treatment period is defined from the signed informed consent up to the first dose of double-blind IMP injection.
- Treatment Emergent Adverse Event (TEAE) period is defined as the time from the first dose of double-blind IMP injection to the last dose of IMP injection + 70 days (10 weeks) as residual effect of treatment is expected until 10 weeks after the stop of double-blind IMP.
- Post-treatment period is defined as the time starting the day after the end of the TEAE period up to resolution/stabilization of all SAE and AESI, whichever comes last.

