10.1.2.5 Week 32 / 10 weeks after last IMP injection (phone call)

- Record concomitant medication, noting also whether the patient has started a commercially available PCSK9 inhibitor
- Collect information on AEs (if any)

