The incidence of premature treatment discontinuation (irrespective of the reason) and premature treatment discontinuation due to AEs will be presented graphically by treatment group on randomized and treated patients (as randomized), using Kaplan-Meier method.

The incidence of premature study discontinuation (irrespective of the reason) and premature study discontinuation due to AEs will be presented graphically by treatment group on randomized and treated patients (as randomized), using Kaplan-Meier method.

Patients with insufficient post-treatment follow-up will be described on the safety population by treatment group. A patient is considered with insufficient post-treatment follow-up or without post-treatment follow-up at the end of the study in the following cases:

- If the patient is not assessed at the post-treatment follow-up call or any post-treatment visit, unless patient died before, or
- If the last post-treatment visit is less than 9 weeks after the last double-blind injection.

All major deviations potentially impacting efficacy analyses, randomization, and drug-dispensing irregularities, and other major or critical deviations will be summarized in tables giving numbers and percentages of deviations by treatment group. Patients excluded from the ITT/mITT population will be listed as well as patients with major deviations potentially impacting efficacy analyses not resulting in exclusion from ITT/mITT population. These deviations are listed in the data review and surveillance plan.

Additionally, the following analysis populations will be summarized by treatment group:

- Randomized population;
- Efficacy population: ITT population and mITT;
- Safety population;
- [REDACTED]
- ADA population.

Definitions of the study populations are provided in [Section 2.3](#).

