2.5.4 Windows for time points

Data analyzed by time point (including efficacy, laboratory safety data, vital signs, [REDACTED] ADA) will be summarized using the analysis windows given in [Table 2](#). These analysis windows will be applicable for all analyses, and they are defined to provide more homogeneous data for time point-specific analyses.

Table 2 - Analysis windows definition

Time point	Targeted study day	Analysis window in study days
Week 4	29	15 to 42
Week 8	57	43 to 70
Week 12	85	71 to minimum (98; study day corresponding to the first injection with IMP from kit allocated at up-titration IVRS contact)
Week 20	141	127 to 154
Week 24	169	155 to 182
Week 32	225	211 to 238

Study days are calculated from the day of first double-blind IMP, the day of first double-blind injection being Day 1. For randomized but not treated patients, Day 1 is the day of randomization.

If multiple valid values of a variable exist within an analysis window, the nearest from the targeted study day will be selected. If the difference is a tie, the value after the targeted study day will be used. If multiple valid values of a variable exist within a same day, then the first value of the day will be selected when time is available, else the scheduled visit will be selected.

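### Visit 8 is tied both to Day 225 ± 7 and to the last injection, so an in-window last safety call can come 63 days after an on-time last dose (60 or 56 days if it is late), against a 70-day TEAE period

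*Protocol*

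**What the plan says.** **Length of the observation window.** Protocol 9.1.2 starts the TEAE period at the first double-blind dose and extends it as follows: "to the last dose of IMP injection + 70 days (10 weeks) as residual effect of treatment is expected until 10 weeks after the stop". SAP 2.1.4 repeats this.

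**When the last contact takes place.** The Protocol synopsis lists "V8: (Week 32 [Day 225 ±7 days]): telephone contact (safety assessment"), and Protocol 10 confirms that "The window period for Weeks 4, 20, and 32 is ± 7 days". Protocol 10 also keeps later visits on the original schedule when one visit date moves. The heading of Protocol 10.1.2.5 reads "Week 32 / 10 weeks after last IMP injection (phone call"), and the flow chart column for Visit 8 carries the same double label.

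**When the last dose is given.** The synopsis states: "Duration of study treatment will be 24 weeks with the last injection administered at Week 22". Protocol 8.1.2 accepts injections within 3 days of schedule. For an injection delayed by mistake or other circumstances by "less than or equal to 7 days from the missed date, then the patient should administer the delayed injection".

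**When AE collection ends.** Flow chart note f ends it at Week 32, and Protocol 9.1.2.1 ends it at the last scheduled visit. Protocol 6.2.1 asks the investigator to document events within 70 days of the last dose, but only those known to the investigator, and presents the Week 32 call as the means of ensuring this. Protocol 10.1.2.4 adds a Week 24 reminder to report events up to 70 days after the last dose.

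**How the SAP uses the window.** SAP 2.4.6.1 gives a patient without an event person-time equal to the full TEAE period, and its Kaplan-Meier analyses censor at the end of that period. SAP 2.2 classes follow-up as insufficient if there is no post-treatment contact, or "If the last post-treatment visit is less than 9 weeks after the last double-blind injection".

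**The concern.** The call exists to cover the 70 days after the last dose, but its calendar window is not constrained by that dose. A site can follow the Day 225 ± 7 rule exactly and still speak to the patient before the TEAE period has ended, with no further contact scheduled. Events in the remaining days are recorded only if the patient volunteers them or the investigator hears of them by another route.

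Safety and tolerability form a primary objective. Days on which nobody asked would enter the rate denominators and the Kaplan-Meier risk sets as if they had been observed free of events. The SAP's own check on follow-up would not reveal the commonest form of the shortfall, which is an early call after an on-time dose.

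**Working it through.** **Inputs.** SAP 2.5.4 sets the day count, "the day of first double-blind injection being Day 1", so Week w is Day 7w + 1. The last planned injection is at Week 22 (synopsis). The call is on Day 225 ± 7, that is Day 218 to Day 232 (synopsis, flow chart, Protocol 10). Injections may be 3 days early or late, and a missed one may be made up to 7 days late (Protocol 8.1.2). The TEAE period ends 70 days after the last dose (Protocol 9.1.2). The SAP 2.2 limit is 9 × 7 = 63 days.

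**The plan's own figure.** Week 22 is 7 × 22 + 1 = Day 155. Week 32 is 7 × 32 + 1 = Day 225. The gap is 225 − 155 = 70 days, so the 10-week label is reproduced exactly, with nothing to spare.

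**Follow-up at the edges of the windows.** Days of follow-up = call day − last injection day. Shortfall = 70 − follow-up.

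| Last injection | Day | TEAE period ends | Call Day 218 | Call Day 225 | Call Day 232 | Shortfall, Day 218 call | Day 218 call flagged by SAP 2.2? |
|---|---|---|---|---|---|---|---|
| 3 days early | 152 | Day 222 | 66 | 73 | 80 | 4 | no |
| on time | 155 | Day 225 | 63 | 70 | 77 | 7 | no |
| 3 days late | 158 | Day 228 | 60 | 67 | 74 | 10 | yes |
| 7 days late, made up | 162 | Day 232 | 56 | 63 | 70 | 14 | yes |

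As a share of the 70 days, the largest shortfalls in the last three rows are 7/70 = 10%, 10/70 = 14.3% and 14/70 = 20%.

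**What the SAP check misses.** Follow-up of 63 to 69 days is shorter than the TEAE period but is not flagged. With an on-time dose, that is every call on Days 218 to 224 (218 − 155 = 63; 224 − 155 = 69). An on-schedule Day 225 call after a dose 7 days late (63 days) also passes.

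**Effect on person-time.** For a patient without an event, the TEAE period counted from Day 1 is 225, 228 or 232 days long (dose on time, 3 or 7 days late). With a Day 218 call, the days not asked about are at most 7/225 = 3.1%, 10/228 = 4.4% and 14/232 = 6.0% of that patient's denominator.

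**The case against.** Much can be said for the plan.

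- **The injection anchor is partly written already.** A reader might infer that the call has no link to the last dose. The flow chart and Protocol 10.1.2.5 both name that link, and Protocol 10.3.4 places the final call 10 weeks after discontinuation for early stoppers who leave the schedule. The defect is two anchors that can disagree, not a missing one.
- **56 days is not the fully compliant case.** It needs the latest make-up injection, outside the ± 3 day window, together with the earliest call. Within the injection window the minimum is 60 days, and with on-time dosing it is 63.
- **The SAP does not pass the worst cases.** It flags both 56 and 60 days. Its 9-week limit equals the planned 10 weeks less the permitted 7 days, so it is consistent with the visit window. It is not consistent with the 70-day TEAE period.
- **Reporting does not stop at the call.** The 70-day documentation duty and the Week 24 reminder remain. Pregnancy is reportable to 70 days (Protocol 10.4.1.3), and related SAEs learned of after study end must be reported (Protocol 10.4.3). What is lost is active enquiry. However, the duty covers only events known to the investigator, and note f and Protocol 9.1.2.1 point to an earlier end.
- **How many patients are affected is unknown.** A reader might compute 7 of 15 permitted days, or 47%, for on-time dosing. That assumes calls spread evenly over the window, which the documents do not support. On the same assumption the mean gap is (1 + 2 + … + 7)/15 = 1.9 days, or 2.7% of 70.
- **The consequence is limited.** The window is the same in both blinded arms, and Protocol 11.4.3 plans no formal testing of safety.

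These points limit the size of the gap but do not close it: an on-time dose and an in-window call are enough to leave part of the TEAE period without active enquiry.

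**Conclusion.** The point stands as a mismatch between the contact schedule and the observation window. For patients who complete treatment, an in-window Visit 8 call can leave up to 7 days of the TEAE period without active enquiry after an on-time last dose, up to 10 days when dosing stays within ± 3 days, and up to 14 days after a dose made up 7 days late. The SAP counts those days as observed and does not flag follow-up of 63 to 69 days.

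The weight is minor to moderate. The gap is short, passive reporting continues through it, the same rule applies to both arms, and nothing in the documents shows an effect on a comparison between them.

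The figures assume that Day 1 is the first injection, that the injection schedule is not shifted by the Week 0 window, and that sites treat Day 225 ± 7 as the operative rule where the two labels differ. If sites instead apply the 10-week label strictly, the gap disappears. The documents do not say which label takes precedence.

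**What to change.** 1. In the flow chart, the synopsis assessment schedule, Protocol 10 and Protocol 10.1.2.5, require the Visit 8 call no earlier than 70 days after the recorded last injection, with a short positive-only window such as 0 to +7 days. The earliest call is then Day 225, 228 or 232 for a last dose on time, 3 days late or 7 days late. All three lie within the present upper limit of Day 232.
2. Align flow chart note f and Protocol 9.1.2.1 with Protocol 6.2.1 and 10.1.2.4, so that AE collection runs to the last dose plus 70 days.
3. In SAP 2.2, change the insufficient-follow-up threshold from 9 to 10 weeks.

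**Cost.** A minor protocol amendment and one number in the SAP, with still a single call. A call that would have been made on Day 218 moves later by at least 7, 10 or 14 days in the three dosing cases. In the extreme case (dose on Day 162, call at the end of a +7 day window) it moves to 162 + 77 = Day 239, which is 21 days later and 7 days beyond the present limit. More patients may be listed as having insufficient follow-up, because 63 to 69 days would now count.
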